8.2.2.6 GVHD-free survival (GFS)

GFS will be defined as the elapsed time between the date of transplant until GVHD related death. Duration of GVHD-free survival will be measured as in Section 7.9.7.

GVHD-free survival will be compared between the treatment groups using Log-rank test and Kaplan-Meier methods will be used to depict the survival curves.

8.3 Supportive Analysis

The PP population will be used for the supportive analysis.

To assess the consistency of the Primary Analysis results, supportive analysis will be conducted using the Per Protocol (PP) population. Statistical methodology for the supportive analyses will be the same as that of the primary analysis, with the exception of the analysis population used.

8.4 Analysis of Safety Data

The Safety population will be used for the analysis of safety assessments.

For continuous variables data will be summarized using n, mean, Standard Deviation (SD), minimum and maximum values. For categorical variables data will be summarized using frequency and percentage. No inferential statistics are planned.

8.4.1 Adverse Events

Adverse events will be coded using Medical Dictionary for Regulatory Activities (MedDRA). TEAEs are defined as events with an onset on or after the first treatment. TEAEs will be summarized by treatment group, System Organ Class, and preferred term. The following TEAE summaries will be provided:

[figure not shown]
- Overall TEAEs
- TEAEs by severity grade

• TEAEs by relationship to study treatment.

In addition, separate summaries of SAEs, and AEs resulting in discontinuation of study treatment will be presented.

8.4.2 Tolerability of repeated subcutaneous administration as assessed by Visual Analogue Scale All data from tolerability assessments of repeated subcutaneous administration of PRO 140 as assessed by study participants (using Visual Analogue Scale, as presented in Figure 8-1: Visual Analog Scale below) and by investigator-evaluation of injection site reactions will be summarized using n, mean, Standard Deviation (SD), minimum and maximum values.

Figure 8-1: Visual Analog Scale

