# 1.4 SUMMARY OF PRIOR PRE-CLINICAL AND CLINICAL STUDIES

### 1.4.1 Pre-Clinical Studies with PRO 140

*In vitro* and *in vivo* preclinical studies have been conducted to determine the pharmacokinetic, immunogenicity, and toxicity profiles of PRO 140 following IV and SC administration. Several acute and chronic toxicity studies have been conducted to support the clinical development plan.

Acute toxicity of PRO 140 was evaluated in New Zealand rabbits, following IV administration of 5 or 15 mg/kg. Chronic toxicity was evaluated in cynomolgus monkeys following biweekly administration of IV doses up to 10 mg/kg for six months and biweekly administration of various SC doses up to 50 mg/kg for 24 weeks. The drug was generally well tolerated. Biweekly administration of IV doses up to 10 mg/kg for six months resulted in minimum to mild lymphoid hyperplasia in assorted lymph nodes and spleen, which was considered an expected immune response to a foreign protein. Biweekly administration of SC doses up to 50 mg/kg for 24 weeks resulted in minimum injection-site reactions (minimal, multifocal, mononuclear cell infiltrates in the subcutis), which were considered due to an inflammatory response to the injected antigen. Monkeys tolerated treatment with PRO 140 for 24 weeks without evidence of local or systemic toxicity. PRO 140 caused no mortality, cageside observations, in-life injection-site observations, or gross pathologic findings. Chronic treatment with PRO 140 did not affect body weight, food consumption, hematology, clinical chemistry or coagulation parameters.

Both IV and SC administration resulted in elimination half-lives of approximately 200 hours, and overall exposure increased with increasing doses. Following SC administration of PRO 140 in monkeys, the maximal concentration ( $C_{max}$ ) was achieved within 56 hours and bioavailability for PRO 140 after SC dosing was approximately 70%.

CONFIDENTIAL Page 38 of 108

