#### 4.3 FOLLOW-UP PHASE

## 4.3.1 Follow-Up Visit 1

The follow-up visit 1 will occur two (2) weeks after the last treatment visit. The following assessments will be performed at the follow-up visit 1, unless otherwise specified:

- Assess for any Adverse Events and changes in Concomitant medications (section 9 and 7.5),
- Vital Signs (section 7.9),
- ECOG performance status (section 7.10)
- Collection of Blood Specimens for
  - o CBC w/diff (section 7.11.1)
  - o Serum biochemistry (section 7.11.2)
- ECG (section 7.7)
- Grading GVHD skin, gut, liver (section 7.17)

### 4.3.2 Follow-up Visit 2

The follow-up visit 2 will occur one year after the first treatment visit. The following assessments will be performed at the follow-up visit 2, unless otherwise specified:

- Assess for any Adverse Events and changes in Concomitant medications (section 9 and 7.5),
- Vital Signs (section 7.7),
- Collection of Blood Specimens for:
  - o T-cell and myeloid chimerism (section 7.11.5).

CONFIDENTIAL Page 62 of 108

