## 5.2.1 Data Collected for Withdrawn Subjects

Investigators considering discontinuing study treatment should contact the medical monitor prior to such discontinuation. Patients who have study treatment discontinued will continue to be followed, per protocol, whenever possible. Patients who have study treatment

CONFIDENTIAL Page 63 of 108

discontinued due to a serious adverse event will be followed until resolution or stabilization of the event.

In the event that a subject is withdrawn from the study at any time due to an adverse event or serious adverse event (SAE), the procedures stated in Section 9.1.1 or 9.2.1, respectively must be followed.

Every attempt should be made to collect follow-up information. The reason for withdrawal from the study will be recorded in the source documents and on the appropriate page of the eCRF.

Before a subject is identified as lost-to-follow up, the site should make all reasonable efforts to contact the subject. These attempts must be documented and should include at a minimum one phone call and one certified letter.

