#### 7.13 PRO 140 ADMINISTRATION

PRO 140 will be administered -2/-3 days before the stem cell infusion, on the day of stem cell infusion (Day 0) and thereafter on days 7, 14, 21, 28, 42, 56, 70, 84 and 98 as per the study schedule of assessments (Table 4-1).

Refer to section 6.4 for details on the procedure of PRO 140 administration.

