# 9.1.1 Reporting of Adverse Events

Report initiation for all AEs and SAEs will begin at the time of the first treatment and continue up until the final study visit (i.e. up to the Follow-up visit). All events will be followed to resolution or until 30 days after the subject completes the study. A final assessment of outcome will be made at that time.

All AEs must be recorded in the subject's medical records and on the eCRFs. AEs will be reported using customary medical terminology along with the following information: the onset and end dates, whether the event is considered to be a SAE (see section 9.2), the impact the event had on study treatment (see section 9.1.2), the CTCAE grade (intensity) of the event (see section 9.1.3), the causality of the event (see section 9.1.4), whether treatment was given as a result of the event (see section 9.1.5), and the outcome of the event (see section 9.1.6).

[figure not shown]

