2.3 Study Duration

A subject will be in this trial at maximum of around 56 weeks.

- **Screening Phase:** up to 4 weeks (28 days).
- Treatment Phase: up to 14 weeks \pm allowed windows (up to 14 treatments).
- Follow-up Phase: up to one year after first treatment visit (T1), approx. 38 weeks from end of treatment visit].

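### TEAEs have a start but no end, so about 73% of the days counted as treatment-emergent fall after the last scheduled dose, and late background events can blur an acute on-drug difference

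*SAP*

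**What the plan says.** - **Definition.** SAP 8.4.1: "TEAEs are defined as events with an onset on or after the first treatment". Protocol 8.7.6.1 uses the same definition. Neither document gives a limit in days after the last dose, or a split between on-treatment and post-treatment events.
- **Dosing.** After Day 0, protocol 7.13 schedules PRO 140 "thereafter on days 7, 14, 21, 28, 42, 56, 70, 84 and 98".
- **Collection.** Protocol 9.1.1 starts AE and SAE reporting at the first treatment, to "continue up until the final study visit (i.e. up to the Follow-up visit". Protocol 4.3.2 says "The follow-up visit 2 will occur one year after the first treatment visit" and lists for that visit: "Assess for any Adverse Events and changes in Concomitant medications (section 9 and 7.5". The schedules of assessments in both documents mark adverse events at Follow-up Visit 2 (Day 365 ± 14). SAP 2.3 puts the end of follow-up at "approx. 38 weeks from end of treatment visit".
- **Early stoppers.** Protocol 5.2.1: "Patients who have study treatment discontinued will continue to be followed, per protocol, whenever possible".
- **Tables.** SAP 8.4.1 plans TEAEs overall, by severity and by relationship, with system organ class and preferred term, plus SAEs and AEs leading to discontinuation of study treatment. None of these is by period. SAP 8.4 plans no inferential statistics for safety.

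**The concern.** A treatment-emergent table is meant to show what happens while subjects are exposed to the drug or shortly afterwards. Here the rule also counts anything that starts in the eight to nine months after the last scheduled dose. In this population that period has its own events: the Background section of the protocol (1.2) places chronic GVHD after Day 100 and says that it can persist for years. If such events occur at similar rates in both arms, they raise both percentages and narrow the gap left by an acute effect on drug.

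Safety and tolerability is the secondary objective. The comparison is descriptive and rests on 30 subjects per arm, so a reader of the main TEAE tables has only the percentages to go on. The plan fixes other outcomes in time: the acute GVHD endpoints and the relapse rate are all by Day 100. The TEAE tables have no such limit.

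**Working it through.** **1. Reproduce the plan's own figure.** From the last scheduled dose (Day 98) to Follow-up Visit 2 (Day 365): 365 − 98 = 267 days; 267/7 = 38.1 weeks, which agrees with the 38 weeks in SAP 2.3. In months, 267/30.44 = 8.8. With the visit windows (last dose Day 95 to 101, final visit Day 351 to 379) the range is 250 to 284 days, or 8.2 to 9.3 months.

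**2. Share of the TEAE window after the last dose.** First dose at Day −3: the window is 365 + 3 = 368 days, and 267/368 = 73%. A Day −2 start gives 267/367, also 73%. A subject who stops after the first dose but is followed to Day 365 has up to 368 days (about 12 months) off drug, all counted as treatment-emergent.

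**3. What an end date would remove.** The only half-life in the documents is from monkeys (protocol 1.4.1): "Both IV and SC administration resulted in elimination half-lives of approximately 200 hours". Five half-lives are 5 × 200/24 = 41.7 days, which ends at about Day 140. The cut-offs below are assumptions.

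| Days after the Day 98 dose | Days no longer counted | Share of 368 |
|---|---|---|
| 14 | 253 | 69% |
| 30 | 237 | 64% |
| 42 | 225 | 61% |
| 90 | 177 | 48% |

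**4. Illustration of the blurring.** Let p be the proportion with an event by the cut-off and q the later incidence, equal in both arms, among those still event-free. The tabulated proportion is p′ = p + (1 − p)q. The difference between arms is therefore multiplied by (1 − q), and the ratio moves towards 1.

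The documents give no value for q. Assume first that the control arm's rate from Day −3 to Day 140 (143 days) continues unchanged in both arms for the remaining 225 days, so q = 1 − (1 − p_control)^(225/143). The last two rows multiply that late hazard by 0.5 and 0.25.

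| Control v PRO 140 by Day 140 | Late hazard | q | To Day 365 | Difference (points) | Ratio |
|---|---|---|---|---|---|
| 5% v 10% | unchanged | 0.078 | 12.4% v 17.0% | 5.0 → 4.6 | 2.0 → 1.37 |
| 10% v 20% | unchanged | 0.153 | 23.7% v 32.2% | 10.0 → 8.5 | 2.0 → 1.36 |
| 20% v 40% | unchanged | 0.296 | 43.7% v 57.8% | 20.0 → 14.1 | 2.0 → 1.32 |
| 10% v 20% | half | 0.080 | 17.2% v 26.4% | 10.0 → 9.2 | 2.0 → 1.54 |
| 10% v 20% | quarter | 0.041 | 13.7% v 23.2% | 10.0 → 9.6 | 2.0 → 1.70 |

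Setting q directly, with 20% v 40% early: q = 10%, 30% or 50% gives 28% v 46%, 44% v 58% or 60% v 70%, so the difference falls from 20 to 18, 14 or 10 points.

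**5. Scale against sampling error.** With 30 per arm, a 10.0-point difference is 3.0 subjects and an 8.5-point difference is about 2.5. The standard error of 10% v 20% is √(0.1 × 0.9/30 + 0.2 × 0.8/30) = 0.091, about 9 points.

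**The case against.** **The size is easily overstated.** The SAP reports percentages, not ratios, and in the main example the difference moves by only 1.5 points against a standard error of about 9. A constant late hazard is also generous: the early period contains myeloablative conditioning, methotrexate and the main risk period for acute GVHD. This stands. The direction follows for any acute effect with an equal later background, but the size is not established.

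**Other tables separate some events.** A reader might infer that every drug signal is diluted. The documents do not support that. AEs leading to discontinuation of study treatment cannot arise after dosing ends, relapse is fixed at Day 100, and injection-site reactions, laboratory values and ECGs have their own summaries. The by-relationship table separates events in part, though only by investigator judgement. A delayed drug effect would not be diluted at all. What remains affected is the overall, system organ class and preferred term, and severity tables.

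**Collection might be read as ending at Day 112.** Protocol 9.1.1 speaks of a single follow-up visit, and protocol 5.1 sets completion at the 2-week follow-up. On that reading only 14 of 115 days (12%) would be off drug. But protocol 4.3.2 and both schedules require AE assessment at one year, and AEs are also recorded at unscheduled visits. The ambiguity is itself a reason to state an end.

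**The split can be made later.** Onset dates are recorded and all data are listed, so nothing is lost. That is true, but a cut-off chosen after unblinding is open to the charge that the data drove it.

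**A ready-made cut-off is tempting.** The 30 days in protocol 9.1.1 might be taken as one. They are the time for following reported events to resolution after study completion, not an onset window after the last dose, so they support no TEAE limit. Nor do the documents show that events after about Day 140 are unrelated to exposure. No human half-life is given, and the human finding in protocol 1.4.3.5 (receptor occupancy above 85% for 29 days) comes from single IV doses, a different route and regimen.

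**Conclusion.** The point holds as a gap in the definition. Under the rule as written, onsets up to about 267 days after the Day 98 dose count as treatment-emergent, and no planned table shows them apart. For subjects who take that dose, 73% of the window lies after it, and more for early stoppers who are still followed. These figures rest only on the documents' own visit days.

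That late background events can blur an acute on-drug difference is a sound inference, on the assumption that such events occur about equally in both arms. How much they do so is unknown. The illustrated fall from 10.0 to 8.5 points (ratio 2.0 to 1.36) depends on an assumed constant background rate and shrinks with a lower late hazard. The gap should be closed because closing it is cheap and changes what the main safety tables show, not because a large loss has been demonstrated.

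**What to change.** Before unblinding:

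1. In SAP 8.4.1, end the TEAE period a stated number of days after each subject's last dose. The sponsor should set and justify the length from PRO 140 exposure data. About 42 days (5 × the 200 h monkey half-life) is one example, with its species limitation stated.
2. Tabulate events with later onset, to Day 365, separately as post-treatment events by arm.
3. Keep all SAEs and deaths to Day 365 in their own table, so that bounding the TEAE period hides nothing.
4. Align protocol 8.7.6.1, which carries the same open-ended definition, or document the departure in the SAP.

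The cost is one extra table and a documented change to the definition. No data collection changes and no event is lost.

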## 7.16 PAIN ASSESSMENT USING VISUAL ANALOG SCALE (VAS)

Tolerability of repeated subcutaneous administration of PRO 140 is evaluated based on assessment of subject-perceived injection site pain using the Pain Visual Analog Scale (VAS). Subjects will be asked to mark the point that best represents the average pain intensity at the injection site over the past week on a horizontal line (100 mm in length) anchored by the following word descriptors at each end, "no pain" on the left side and "pain as bad as it could possibly be" on the right side of the line. The subject marks on the line or by pointing to a position on the line the point that they feel represents their perception of their pain state. The VAS score is determined by measuring in millimeters from the left-hand end of the line to the point that the patient marks. The first VAS assessment will occur prior to study treatment administration at visit T2.

Figure 7-1: Sample Visual Analog Scale

CONFIDENTIAL Page 76 of 108

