## 8.7.6.2 Tolerability Assessment

All data from tolerability assessments of repeated subcutaneous administration of PRO 140 as assessed by study participants (using Visual Analogue Scale) and by investigator-evaluation of injection site reactions will be summarized.

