# 17.1 APPENDIX I: ADVERSE EVENTS OF SPECIAL INTEREST: INJECTION SITE REACTIONS The following table should be used to characterize injection-site reactions and provide appropriate grading of severity.

Injection-site Reactions				
Parameter	Grade 1 (Mild)	Grade 2 (Moderate)	Grade 3 (Severe)	Grade 4 (Potentially life- threatening)
Injection-site pain	Pain without touching or pain when area is touched: no or minimal limitation of use of limb	Pain without touching or pain when area is touched limiting use of limb OR causing greater than minimal interference with usual social and functional activities	Pain without touching or pain when area is touched causing inability to perform usual social and functional activities	Pain without touching or pain when area is touched causing inability to perform basic self-care function OR hospitalization (other than emergency room visit) indicated for management of pain/tenderness
Characterization of the injection site, if not normal	Erythema OR induration of 5x5 cm - 9x9 cm (or 25 cm2-81 cm2)	Erythema OR induration OR Edema >9 cm any diameter (or >81 cm2)	Ulceration OR secondary infection OR Phlebitis or Sterile abscess OR drainage	Necrosis (involving dermis and deeper tissue)
Pruritus associated with injection	Itching localized to injection site AND relieved spontaneously or <48 hours of treatment	Itching beyond the injection site but not generalized OR itching localized to injection site requiring ≥48 hours treatment	Generalized itching causing inability to perform usual social and functional activities	N/A
Bleeding	Initial bleed that does not exceed bandage and spontaneously stops	Bleeding that exceeds bandage and spontaneously stops	Continued bleeding that requires change of dressing and alternative injection site	N/A
Absorption of drug	Minor elevation of skin at injection site but no leakage of injection material	Leakage at injection site ceases with decrease in injection rate	Leakage at injection site that does not cease with decrease in injection rate	

CONFIDENTIAL Page 107 of 108

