8.4.10 Injection Site Reactions

All data from injection site reaction assessments of the repeated subcutaneous administration of PRO 140 will be descriptively summarized.

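### SAP 8.4.2 summarises graded injection-site reactions with statistics for continuous data, against the rule in SAP 8.4, so the table does not show how many subjects had each grade

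*SAP*

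**What the plan says.** - **SAP 8.4 (Analysis of Safety Data)** sets one rule per variable type: "For continuous variables data will be summarized using n, mean, Standard Deviation (SD), minimum and maximum values", and "For categorical variables data will be summarized using frequency and percentage". No inferential statistics are planned for safety.
- **SAP 8.4.2**, whose heading names only the VAS, treats the VAS together with the data assessed "by investigator-evaluation of injection site reactions will be summarized using n, mean, Standard Deviation (SD), minimum and maximum values".
- **SAP 8.4.10 (Injection Site Reactions)** says: "All data from injection site reaction assessments of the repeated subcutaneous administration of PRO 140 will be descriptively summarized". It lists no statistics.
- **Protocol 8.7.6.2 (Tolerability Assessment)** is equally open; data assessed "by investigator-evaluation of injection site reactions will be summarized".
- **Protocol 17.1 (Appendix I)** fixes the scale: "The following table should be used to characterize injection-site reactions and provide appropriate grading of severity". It grades five parameters: pain, appearance of the site, pruritus, bleeding and absorption of drug. Pain and appearance run from Grade 1 to Grade 4. For pruritus and bleeding Grade 4 is marked not applicable, and for absorption the Grade 4 cell is blank.
- **Protocol 7.16** fixes the scale of the other measure, on a 100 mm line: "The VAS score is determined by measuring in millimeters from the left-hand end of the line to the point that the patient marks".

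**The concern.** The statistics in SAP 8.4.2 are the list that SAP 8.4 reserves for continuous variables, here applied to an ordinal grade. On the Appendix I scale for site appearance, for example, Grade 2 is a larger area of redness, hardening or swelling and Grade 3 includes ulceration. The distance between grades has no fixed meaning, and a mean of 0.5 describes no subject's experience.

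Tolerability of repeated injection is the first safety assessment listed in both documents, and safety and tolerability form the secondary objective. Protocol 9.1.8 makes reactions directly related to the injection adverse events of special interest. Because safety is analysed descriptively only, the summary table is the analysis. The reader of that table needs to know how many subjects in each arm had a mild, moderate or severe reaction. SAP 8.4.2 is the only place that names statistics specifically for these reactions, and its list does not include that count.

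**Working it through.** **Step 1: compare the rules.** The plan gives no figure on this point, such as an expected reaction rate, so there is none to reproduce.

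| Measure | Scale | Rule in SAP 8.4 | Rule in SAP 8.4.2 | Consistent? |
|---|---|---|---|---|
| Pain VAS | 0 to 100 mm | n, mean, SD, min, max | n, mean, SD, min, max | Yes |
| Injection-site reactions | Ordinal grade, five parameters | Frequency and percentage | n, mean, SD, min, max | No |

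SAP 8.4.10 is compatible with either rule, so it does not settle which one a programmer should follow.

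**Step 2: what the 8.4.2 list can and cannot show.**

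Inputs: 30 subjects per arm (SAP 4). The unit is the worst grade per subject, with 0 for no reaction. The unit and all grade counts below are assumptions for illustration.

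With n_g subjects at grade g:

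- mean = Σ g·n_g / 30
- SD = √[(Σ g²·n_g − (Σ g·n_g)²/30) / 29]

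*The maximum does carry information.*

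- Three subjects at Grade 3, 27 at 0: mean = 9/30 = 0.30; SD = √[(27 − 81/30)/29] = 0.915; maximum 3.
- Nine subjects at Grade 1, 21 at 0: mean = 9/30 = 0.30; SD = √[(9 − 81/30)/29] = 0.466; maximum 1.

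The means agree, but the SD and the maximum tell these two arms apart.

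*The full list can still hide the counts.*

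| Arm | Grades 0/1/2/3 | Σ g·n_g | Σ g²·n_g | Grade 3, n (%) |
|---|---|---|---|---|
| A | 23/0/6/1 | 0 + 12 + 3 = 15 | 0 + 24 + 9 = 33 | 1 (3.3%) |
| B | 22/3/3/2 | 3 + 6 + 6 = 15 | 3 + 12 + 18 = 33 | 2 (6.7%) |
| C | 21/6/0/3 | 6 + 0 + 9 = 15 | 6 + 0 + 27 = 33 | 3 (10.0%) |

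In each arm the mean is 15/30 = 0.50, the SD is √[(33 − 225/30)/29] = √(25.5/29) = 0.938, the minimum is 0 and the maximum is 3. The five statistics are identical. The number with Grade 2 or higher is 7, 5 and 3, and the number with any reaction is 7, 8 and 9. Frequencies separate the arms at once; the 8.4.2 output cannot.

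**Step 3: do other planned outputs supply the counts?**

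- *TEAEs by severity grade (SAP 8.4.1):* in part. Protocol 9.1.3 grades adverse events by CTCAE v4.03, not by Appendix I. The table is organised by system organ class and preferred term rather than by the five parameters. Under Protocol 9.1, findings that are not clinically significant are not recorded as adverse events, so some mild reactions may not reach it.
- *Subject listings (SAP 8):* they contain every grade but give no summary by arm.

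**The case against.** The strongest reply is that this is one loosely drafted sentence. The heading of 8.4.2 names only the VAS, so the VAS statistics may simply have been carried over to the reactions. SAP 8.1 and 8.4 both tie the summary to the variable type, 8.4.10 is a dedicated section, and nothing says that 8.4.2 overrides them. A careful programmer could produce frequency tables under 8.4.10. This is a fair reading and a reason to rate the point low. It does not remove the conflict, because the one sentence that names statistics for these reactions names the wrong ones.

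A reader might infer something stronger: that the SAP averages severe reactions away. The documents do not support that.

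- The 8.4.2 list includes the maximum, so a single Grade 3 reaction shows as a maximum of 3.
- Reactions directly related to the injection are adverse events of special interest (Protocol 9.1.8) and enter the TEAE table by severity. SAP 8.4.1 also plans a separate summary of adverse events that lead to discontinuation of treatment.
- Protocol 9.1.10 sends the data to the DMC after two Grade 3 toxicities assessed as drug-related.
- All data are listed by subject.

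Nor can one say that the mean will lie near zero whatever happens. The SAP does not state the unit of averaging, and the result depends on it. Suppose two subjects of 30 each have one Grade 3 reaction and there are no others, a total of 2 × 3 = 6. The mean is 6/30 = 0.20 by worst grade per subject. It is 6/330 = 0.018 over 30 × 11 = 330 dosing visits, and 6/660 = 0.009 over 660 injections, since each dose is two injections. The last two figures also assume that every subject receives all 11 doses, whereas Protocol 9.1.9 provides for discontinuation after certain Grade 3 or higher events.

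**Conclusion.** Wrong as written, and minor. SAP 8.4.2 contradicts SAP 8.4 for injection-site reactions, and 8.4.10 does not resolve it. What the 8.4.2 summary loses is the number and percentage of subjects at each Appendix I grade; the worst grade remains visible. The TEAE tables and listings make up part of the loss, but not by parameter and Appendix I grade.

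That 8.4.2 contradicts 8.4 rests on the text alone. The size of the loss is shown only by illustration: arms with 1, 2 or 3 Grade 3 subjects among 30 can share all five statistics. Those counts, and the use of worst grade per subject, are assumptions. No efficacy endpoint is affected.

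**What to change.** 1. In SAP 8.4.2, limit n, mean, SD, minimum and maximum to the VAS and refer to 8.4.10 for injection-site reactions.
2. In SAP 8.4.10, state that reactions will be presented as the number and percentage of subjects by worst Appendix I grade, for each parameter (using only the grades defined for that parameter) and overall, by treatment group.

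The cost is two sentences of SAP wording and one table, made before database lock. The grades are already to be collected at each treatment visit, so no protocol or data change is needed.
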